**Statistical Analysis:** *Power analysis and sample size calculation:* The sample size calculation was based on power estimates using our preliminary data on how acute postoperative pain contributes to PPP using the SAS "powerlog" macro. An updated analysis of our multi-center (three) chronic pain after total knee and hip arthroplasty survey study, evaluated one yr postoperatively, provided data for sample size calculation. The one yr follow-up data from this survey provides a conservatively estimate for the incidence of PPP at 6 mo, our primary outcome. To evaluate the effect of acute postoperative pain on incidence of PPP, our multi-center data was stratified based on chronic pain using our PPP criteria. Across the three centers, 259 TKR patients fell within criteria, of which 46 (17.8%) were identified with PPP at one year after surgery. Using a logistic regression, the acute postoperative NRS pain intensity was significant ( $P=0.0005$ ) with an odds ratio of 1.24 for each 1 point increase in acute postoperative NRS pain (95% Wald Confidence limits: 1.098-1.390). The average acute postoperative NRS pain for the entire sample was 5.5 (SD=2.9). Using the data to estimate predicted probability of PPP at the mean acute postoperative pain level, we have an incidence of 15.5% at the mean and 30.3% at the mean plus one standard deviation (NRS=8.4). A power analysis with 90% power and alpha of 0.05, using a logistic regression with no other covariates gives us a required sample size of 130. However, because we plan on utilizing multiple covariates, we estimate the multiple squared correlations at 0.5, raising our sample size estimated to 259. With a 15% dropout rate this values climbs to 298 (round to 300).

**Blinding of data:** To reduce bias, each co-investigator will only be involved in measurements specifically related to their specialization (Pain, Neurophysiologic, Psychosocial or Functional outcomes) and no others.

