### **Detailed Analyses:**

**Primary Aims:** are to investigate the relationships of *risk factors* and the development of PPP at 6 mo post-TKR, through independently predictive (for clinical prediction models, Hypothesis 1) and mediated models (to reveal underlying mechanisms, Hypothesis 2). These risk factors are preop thermal pain sensitivity; anxiety and catastrophizing; postop area of secondary mechanical hyperalgesia and pain intensity.

A. **Independent Risk Factors:** Risk factors will be individually predictive of the PPP (primary endpoint):

*Hypothesis 1 is that greater (↑) preop pain sensitivity, higher levels of preop pain anxiety and catastrophizing, larger areas of secondary hyperalgesia post-TKR and higher postop pain intensity will independently predict increased incidence of PPP at 6 months post-TKR.*

- 1) **Pain Intensity:** Expected Result: (Hypothesis 1): Higher postop pain intensity (↑), will independently predict increased incidence of PPP at 6 mo post-TKR (ex. ↑ postop NRS → ↑ PPP incidence).
- 2) **Neurophysiologic:** Expected Result: (Hypothesis 1): Greater preop pain sensitivity (↑) and larger areas of secondary hyperalgesia ( $\text{cm}^2$ ) post-TKR will independently predict increased incidence of PPP at 6 mo post-TKR (ex. ↑ preop thermal pain sensitivity → ↑ PPP incidence).
- 3) **Psychosocial:** Expected result: (Hypothesis 1): is that greater (↑) catastrophizing (PCS score) will independently predict increased incidence of PPP at 6 months post-TKR (ex. ↑ PCS score → ↑ PPP).
- 4) **Demographics:** Expected result: Patients 65-85 yrs will have a lower incidence of PPP than patients 18-64 yrs.

B. **Mediation Models:** Effects of preoperative factors on development of PPP occur through interrelated neurophysiologic mechanisms:

*Hypothesis 2 is that the effects of preoperative factors on development of PPP occur through interrelated neurophysiologic mechanisms. Thus, it is expected that the area of secondary hyperalgesia post-TKR will mediate links between preoperative pain sensitivity and PPP incidence, as well as mediate links between pain anxiety/catastrophizing and PPP incidence at 6 mo after TKR.*

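### The 90% power for an independent effect of acute pain is unsupported: the covariate step inflates the variance for R² = 0.5 but keeps an apparently unadjusted effect size

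*Combined protocol and SAP*

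**What the plan says.** The sample size is set out in the power paragraph under Statistical Analysis. A three-center survey of knee replacement patients supplies the inputs. Acute pain on the 0–10 scale (NRS) has mean 5.5 and SD 2.9, with an "odds ratio of 1.24 for each 1 point increase in acute postoperative NRS pain". Predicted PPP incidence is given as 15.5% at the mean and 30.3% one SD above it. No covariates are mentioned for the survey model.

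For 90% power and alpha 0.05, sidedness not stated, "using a logistic regression with no other covariates gives us a required sample size of 130". The next step is: "However, because we plan on utilizing multiple covariates, we estimate the multiple squared correlations at 0.5, raising our sample size estimated to 259". Dropout then takes 259 to 298, rounded to 300. (The survey also happened to contain 259 patients.)

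The hypothesis to be served is Hypothesis 1 under Detailed Analyses. Besides preoperative sensitivity, anxiety and catastrophizing, it states that "larger areas of secondary hyperalgesia post-TKR and higher postop pain intensity will independently predict increased incidence of PPP". General statistical analysis plans backward stepwise logistic regression at P<0.05, and the example prediction equation has six terms. Item 3 of Potential Difficulties and Limitations calls the power estimates conservative. No adjusted odds ratio appears anywhere.

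**The concern.** Adding covariates to a logistic model can do two things to the coefficient of acute pain. Its standard error grows because acute pain shares variance with the other terms; dividing by (1 − R²) allows for that. The coefficient itself also changes if the shared part predicts PPP. The plan makes the first allowance and not the second. The crude effect can stand in for the adjusted one only if the covariates sharing half of acute pain's variance have, on balance, no effect on PPP given acute pain.

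The plan's own text points the other way. Hypothesis 1 expects each of the other risk factors to raise PPP. The Significance section links catastrophizing both to higher reported pain and to PPP after knee replacement. A positive link on both sides is the pattern that shrinks an adjusted odds ratio. At stake is what the 90% means: it is offered for the multi-covariate test but is built on an effect that appears to be the crude one.

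**Working it through.** **Inputs from the power paragraph:** 15.5% and 30.3%; SD 2.9; odds ratio 1.24 per point; 90% power; alpha 0.05; R² = 0.5; sizes 130 and 259.

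**1. Effect used.** ln[(0.303/0.697)/(0.155/0.845)] = 0.863 per SD, an odds ratio of 2.37 per SD, or exp(0.863/2.9) = 1.35 per point.

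**2. Reproducing 130 and 259.** For a standard normal predictor, intercept logit(0.155) and slope 0.863, numerical integration of the logistic information gives a per-patient slope variance of about 9.16. For 90% power, two-sided: n = (1.96 + 1.2816)² × 9.16/0.863² ≈ 129.3, so 130. Dividing by (1 − 0.5) gives 258.5, so 259. Both figures come back with the effect still at 0.863. The base figure depends on the formula: Hsieh's 1989 formula gives 122 one-sided or 152 two-sided, and the 1998 formula 108 two-sided.

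**3. Effect of attenuation.** The documents give no covariate effects, so this step is assumption. Summarize the other terms as one standardized score W, correlated √0.5 = 0.71 with acute pain. Hold the crude odds ratio at 2.37 per SD and crude risk at the mean at 15.5%. Roughly, adjusted log odds ratio = 0.863 − 0.71 × ln(odds ratio of W); the table uses the exact solution, which allows for non-collapsibility of the odds ratio. Power = Φ(adjusted log odds ratio/SE − 1.96), with SE from the two-term model's information at n = 259. Examples:
- No effect of W: 0.863/0.253 − 1.96 = 1.45, 93%. The (1 − R²) rule uses the slightly larger SE √(9.16/129.5) = 0.266 and returns the plan's 90%.
- Adjusted odds ratio 2.09: 0.736/0.249 − 1.96 = 1.00, 84%.
- Adjusted odds ratio 1.68: 0.516/0.246 − 1.96 = 0.14, 55–56%.

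| Odds ratio of W per SD (assumed) | Adjusted odds ratio, acute pain, per SD | Two-sided power at 259, formula | Simulation |
|---|---|---|---|
| 1.0 | 2.37 | 93% | 94% |
| 1.1 | 2.22 | 89% | 91% |
| 1.2 | 2.09 | 84% | 85–86% |
| 1.3 | 1.98 | 78% | 80% |
| 1.38 | 1.90 | – | 73% |
| 1.5 | 1.80 | 66% | 66% |
| 1.68 (as strong as acute pain) | 1.68 | 55% | 54–56% |

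One-sided, simulated power is about 97% at 2.37, 91% at 2.09, 82% at 1.90 and 67% at 1.68.

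**4. Sensitivity to R².** With R² = 0.3 instead, and W at 1.1, 1.2, 1.3, 1.5 and 1.68, two-sided power is about 97%, 96%, 94%, 89% and 82%.

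**5. Conflict in the input.** The printed 1.24 per point gives 1.24^2.9 = 1.87 per SD. From odds of 0.155/0.845 that is 25.5% one SD above the mean, not 30.3%. At 1.87 per SD and R² = 0.5, two-sided power at 259 is about 63% (Hsieh 1989) to 73% (simulation) before any attenuation. This is a separate discrepancy, but no power table can be final until it is settled.

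**The case against.** The strongest reply is that no loss of power is demonstrated. Shared variance alone does not shrink an odds ratio, and every shortfall above comes from an assumed W. With no effect of W power exceeds 90%, and at 1.1 it stays near 90%. That stands.

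The R² of 0.5 is also attributed to multiple covariates in general. The Covariates paragraph lists items such as BMI, OA severity, ASA status, duration of surgery and analgesic use. Most are not Hypothesis 1 risk factors and carry no stated direction; for age, the plan expects less PPP in older patients. So Hypothesis 1 makes attenuation likely without entailing it. The 0.5 itself is unsourced, and at 0.3 most of the loss disappears.

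The planned procedure is backward elimination, not a fixed two-term model. In simulation at R² = 0.5, acute pain was retained as significant in about 95%, 91%, 86%, 70% and 60% of runs for W at 1.1, 1.2, 1.3, 1.5 and 1.68. The plan also examines factors individually, where power exceeds 99%. Both are fair, but significance after W has been dropped, or in a one-factor model, is not a test of an effect adjusted for W.

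Finally, that the survey model was unadjusted is an inference: the text does not say so, although its probabilities are indexed by acute pain only. None of this supplies the missing adjusted effect.

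**Conclusion.** The 90% power for an independent effect of acute pain is unsupported. It requires the adjusted odds ratio to stay near 2.37 per SD, a condition that the plan neither states nor justifies and that sits uneasily with Hypothesis 1 and the Significance section. The size of any loss is conditional on the crude odds ratio of 2.37, R² = 0.5, a single summary score for the covariates and a two-sided test. Under those assumptions power runs from about 93% down to about 55% as the adjusted odds ratio falls from 2.37 to 1.68.

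A reader might infer that the study fails to reach 90% power, that the plan's assumptions force a smaller adjusted effect, or that 300 patients are too few. The documents do not support these readings: they give no covariate effects, and weak covariates or a lower R² would leave power near or above 90%. Nor do they say how a null result for acute pain would be interpreted. What they do not support either is the description of the power as conservative: on this point the effect appears to be the more favorable choice.

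**What to change.** Keep 300 patients and revise the power paragraph in this order.

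1. Reconcile the printed 1.24 per point (1.87 per SD, 25.5% one SD above the mean) with the 15.5%/30.3% pair (2.37 per SD, 1.35 per point), and state whether alpha is one- or two-sided. Do not print 2.37 or 1.35 as the design effect before this is done.
2. State whether the survey model included covariates. If it did not, say that the 90% applies to the unadjusted association, or to an adjusted odds ratio equal to the reconciled input at R² = 0.5.
3. Give a short table of power at 259 over smaller adjusted odds ratios and several R² values. If the survey holds covariates, refit it with them and use the adjusted probabilities as input.
4. Withdraw or qualify the statement in item 3 of Potential Difficulties and Limitations that the power estimates are conservative.

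The cost is rewording, a small table and possibly one refit of existing survey data. No patients are added and no planned analysis changes, but the stated power may become less favorable.

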Analgesic Consumption	X	X	X	X	X	X	X	X	X
Knee X-Ray Medical Chart Results	X						X		X
Pain Intensity	X	X	X	X	X	X	X	X	X
Neurophysiologic Assessments	X		X						X
Functional Tests	X		X	X	X	X	X	X	X
Psychosocial tests	X								X

\*ROM will be the only functional test assessed at 36, 48, and 72 hours

**Screening and recruitment feasibility:** A research coordinator/nurse (RN) will screen patients scheduled for Drs. [name] (Co-Investigator), [name], [name], [name] and [name] (participating orthopedic surgeons) to undergo TKR using the criteria detailed below. We will recruit 100 patients/yr. Patient recruitment will be completed within 36 mo; however the 6- mo follow-up extends the study period to a total of 3.5 yrs. If a patient meets study criteria, the RN will contact the patient to obtain verbal consent and assess study eligibility. Selection for inclusion will not be based on race or socioeconomic status.

**Inclusion & exclusion criteria:** *Inclusion Criteria* are: (1) undergoing standard tricompartmental primary TKR; (2) 18- 85 yrs of age; (3) knee to be replaced is the primary source of patient's pain; (4) patient agrees to preoperative and follow-up visits and to comply with the assessment tests; (5) patient consents to standard anesthetic and analgesic protocol, with medical care as deemed necessary by the anesthesiologist, and has no contraindications. (6) Patient has been diagnosed with osteoarthritis. *Exclusion criteria* will include: (1) chronic opioid use  $\geq$  10 mg/day of morphine equivalents within one wk prior to the surgery, and duration of use  $>$  4 wks; (2) history of opioid abuse; (3) inability to understand and communicate with the investigators to complete the study related questionnaires ; (4) patient is planning to undergo another elective joint replacement procedure during the 6-mo period of participation; (5) any co-morbidity which results in severe systemic disease limiting function {as defined by the American Society of Anesthesiology (ASA) physical status classification  $>$  3} (6) taking medication for severe depression .

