**Enrollment & Pre-surgery Assessments:** Prior to pre-operative assessments, up to 8 weeks prior to surgery, written informed consent will be obtained. Demographic data such as age, BMI, ASA status and a physical examination will be performed by PI and RN. All of the assessments below will be coordinated by the RN, in conjunction with the routine preoperative laboratory tests for undergoing TKR. We will obtain an 8.5mL DNA blood sample as well as a 5mL RNA blood sample. A knee radiograph (AP and lateral weight bearing views) will also be reviewed by the study's orthopedic surgeon to determine OA severity (scale) and documented. Patients will be instructed to discontinue non-steroidal anti-inflammatory drugs (NSAIDs) a wk prior to surgery as routine clinical practice. A prescription for tramadol hydrochloride 50 mg tablets with a maximum of 3 tablets /day will be provided to the patients to be taken if the pain in the knee is of moderate-to-severe intensity prior to the surgical date.

All measures selected for this study are established, reliable and validated and listed in order of importance. These measures will be classified into Pain, Neurophysiologic Assessment, Psychosocial and Functional test categories and may be used as predictors, mediators, moderators, or outcome measures, depending on specific hypotheses, and will be assessed at various time points as shown in the study calendar.

**(1) Pain Intensity: Numerical Rating Scale (NRS) of pain intensity:** The NRS score has been selected as the primary instrument to quantify pain intensity. Subjects will be presented by the RN with 11-point NRS, (0 = "no pain" and 10 = "worst pain imaginable"), accompanied by the instructions "Please rate your pain by

indicating the number that best describes your pain on average in the past 2h of the affected knee joint." The NRS will be evaluated at rest, and also with movement (patient-initiated flexion). The NRS is used extensively in clinical trials reported in the orthopedics, pain and surgical literature. Within the pain literature, a NRS <4 is considered mild pain, while a NRS ≥4 is moderate-to-severe pain.

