**(2) Neurophysiologic Assessment:** The following neurophysiologic assessments will be performed at the Department of Anesthesiology Clinical Research Section (Room 1487 Jelke), where the PI or Co-PI ([name]) will supervise the RN in the performance of these tests. These assessments have been performed by the PI and [name] (Co-investigator) for other clinical and basic research respectively.

**(a) Thermal pain stimulation:** Prior to surgery, a heat probe (3x3 cm; TSAll instrument; Medoc®) will be applied 16 cm above the center of the patella as a measure for **thermal pain sensitivity**. Probe temperature will be ramped up from 32° C at a rate of 4°C/sec until 47 °C is reached, and then maintained for 5 sec. After the 5 sec period, subjects will rate pain intensity (0-10 NRS scale). If subject requests removal of probe before 5 sec period due to intolerable discomfort, it will be removed and a maximal value of 10 will be given. The test will be repeated 4 times and the average of the responses will be calculated. This procedure will be repeated on the contralateral leg. **(b) Examination of the knee for peripheral neuropathic pain (StEP)** using the following 9 parameters and calculating a score to determine the presence of neuropathic pain (total score ≥ 4). The StEP will detail the symptoms and signs of the pain in the knee. This test will be performed 5 cm medial and 5 cm rostral to the center of the patella on the un-operated knee as a control and then the operated knee.

- Sympathetic: Recording of skin characteristics (yes/no evaluation of color, sweating, trophic changes)
- Tactile allodynia (touch): Numbness, allodynia or hyperalgesia to von Frey filament stimulation, with corresponding NRS pain intensity
- Tactile hyperalgesia (blunt pressure): Decreased or increased response, with corresponding NRS pain intensity
- Dynamic tactile allodynia (brush movement): Decreased or increased response, with corresponding NRS pain intensity
- Vibration sense (tuning fork): yes/no to decreased response to stimulation at the tibia bone ventral midline, 15 cm below lower point of proposed incision
- Evoked pain (pinprick): decreased or increased response, with corresponding NRS pain intensity
- Non-painful warm stimulus (TSAll instrument, Medoc®): decreased or increased response, with corresponding NRS pain intensity

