- Non-painful cold stimulus (TSAll instrument, Medoc®): decreased or increased response, with corresponding NRS pain intensity
- Mechanical temporal summation: yes/no to increased pain with repetitive von Frey stimulation.

**(3) Psychosocial measures:** These measures will be supervised by the PI and administered by the RN.

**(a) Pain Catastrophizing Scale (PCS):** The PCS will be used to measure catastrophizing. The 13-item measure asks respondents to rate, using a 5-point Likert scale ranging from 0 (*not at all*) to 4 (*all the time*), the degree to which they have certain thoughts and feelings when experiencing pain. Higher scores indicate greater use of catastrophic thinking. The PCS has exhibited strong internal consistency ( $\alpha=0.93$ ), concurrent and discriminant validity, and high test-retest reliability over a 6 wk period ( $r = 0.78$ ). Research suggests that the PCS is responsive to treatment (measure is in public domain-no permission required for study).

**(b) Beck Depression Inventory (BDI-II):** The BDI-II assesses emotional function by measuring the level of depressed mood based on attitudes and symptoms that are common among depressed subjects and uncommon among those not depressed. BDI-II, which has been widely used in pain studies, consists of a 21-item self-report measure of depressive symptoms experienced during the past wk. BDI-II is an update with modifications made to conform scoring to diagnosis as defined by the DSM-IV (permission obtained for study).

**(c) State-Trait Anxiety Inventory (STAI):** STAI has two variations, STAI-state and STAI-trait, and each is a 20-item self-report assessment device, one for state anxiety and one for trait anxiety. The state anxiety score reflects a transient evaluation of anxiety and in particular the current self-report state. Trait anxiety measures a subject's dominant response style although modification can be seen with psychological interventions (permission obtained for study).

**(4) Functional measures:** Measures of the study will be supervised by the PI and administered by RN.

(a) *Knee range of motion (ROM):* The degree of active (patient moving the knee) and passive (movement of the knee with the aid of RN) knee flexion, will be measured using a goniometer. The PI has previously performed ROM measures with the aid of physical therapists.

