#### **Long-term Assessments (same methods used pre-surgery):**

(1) **Pain Intensity:** NRS of the operated knee will be obtained by RN from the patients at the 3 wk, 6 wk, 3 mo and 6 mo scheduled visits.

(2) **Neurophysiologic Assessment** will be performed at the 6 mo scheduled visit.

(a) *Examination of the knee for peripheral neuropathic pain (StEP)*

(3) **Psychosocial Measures:** Beck Depression Inventory will be administered at 6 mo by RN.

(4) **Functional Measures:** ROM, WOMAC and SF-36 questionnaires will be administered at 3 wk, 6 wk, 3 mo and 6 mo.

(5) **Skin Temperature:** Skin temperature will be performed at 6 months

**Patients who have NRS $\geq$ 4 at three wks and beyond:** For patients having NRS $\geq$ 4 at 3 wk and beyond, the oral opioid regime will be continued. If the hydrocodone/acetaminophen regime does not maintain a NRS $<$ 4, then oral long-acting opioids such as time-release oxycodone 10 mg twice/day will be prescribed. The purpose of closely following the analgesics and NRS for the study patients is to ensure that at the 6-mo time point the analgesic consumption is within a standard protocol for all patients, whether they do or do not have PPP. Patients who have persistent pain at the 3 and 6-mo visits will be evaluated by the orthopedic surgeon for prosthetic-related failure. An examination will be performed to evaluate instability of the tibial femoral joint or patellar maltracking. Plain radiographs will be reviewed by the orthopedic surgeons (Co-investigators) for evidence of prosthetic loosening, malposition and patellar maltracking, as well as overall axial alignment to ensure coronal alignment is within the range of neutral to 10 deg of valgus. If this evaluation is negative, an erythrocyte sedimentation rate (ESR) and C-reactive protein (CRP) measurement will be obtained as a screening tool for infection. If these indices are abnormal (ESR $>$ 30 mm/h; CRP $>$ 10 $\mu$ g/mL), an aspiration of the knee will be performed, including a synovial fluid white blood cell count with differential and culture to rule

out infection. These parameters are based on previous work by [name] (Co-investigator) in this specific topic.

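### The plan's only blinding provision separates co-investigators by domain, but the RN role collects data in all four domains and is not masked, so the safeguard does not reach the people who take the measurements

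*Combined protocol and SAP*

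**What the plan says.** The *Blinding of data* paragraph under *Statistical Analysis* is the plan's only blinding provision. For the purpose of reducing bias, it says that "each co-investigator will only be involved in measurements specifically related to their specialization"; it lists four domains (pain, neurophysiologic, psychosocial, functional) and rules out involvement in any other. It does not mention the RN, and it does not mention masking anyone to predictor or outcome values.

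The measurement sections describe who does the work:

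- Under *Screening and recruitment feasibility*, "A research coordinator/nurse (RN) will screen patients". Under *Enrollment & Pre-surgery Assessments*, "All of the assessments below will be coordinated by the RN".
- On the neurophysiologic tests before surgery, the PI or Co-PI "will supervise the RN in the performance of these tests".
- On the psychosocial forms (PCS, BDI-II, STAI): "These measures will be supervised by the PI and administered by the RN".
- On ROM, WOMAC and SF-36: "Measures of the study will be supervised by the PI and administered by RN".
- Under *Long-term Assessments*, which include the 6-month visit: "NRS of the operated knee will be obtained by RN from the patients".

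Under *Acute Postoperative Assessments*, the RN also maps the area of punctate hyperalgesia, supervised by the PI.

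**The concern.** The study tests whether predictors measured before and just after surgery are associated with pain at 6 months. No treatment is compared, so the blinding that matters is that of the assessor: whoever maps hyperalgesia should not know the questionnaire and thermal scores, and whoever obtains the 6-month outcome should not know the predictors.

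Domain separation would help if the people confined to one domain were the people taking the measurements. Here the separation applies to co-investigators, while the RN role runs across all domains. Hypothesis 2 posits a chain from catastrophizing, anxiety or thermal sensitivity, through hyperalgesia area, to PPP. The same role administers the forms, performs the thermal test, maps the area and later asks for the 6-month pain score. Examiner expectation could therefore enter at both links of that chain. A reader of the blinding paragraph alone would not learn this.

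**Working it through.** There is no stated figure to reproduce. The check sets the named collector and supervisor for each measure beside the blinding paragraph.

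| Domain | Measure and role in the analysis | Collector named | Supervisor named |
|---|---|---|---|
| Pain | NRS before surgery; 6-month NRS (basis of PPP) | RN | none |
| Pain | 4-hourly inpatient NRS, 0-72 h (predictor) | none | none |
| Neurophysiologic | Thermal sensitivity (predictor); preoperative StEP | RN | PI or Co-PI |
| Neurophysiologic | Hyperalgesia area (predictor, mediator) | RN | PI |
| Neurophysiologic | 6-month StEP (secondary endpoint) | none; RN inferred because pre-surgery methods are to be reused | none |
| Psychosocial | PCS, STAI (predictors), BDI-II | RN | PI |
| Functional | ROM, WOMAC, SF-36 (primary endpoints of the Secondary Aims) | RN | PI |
| Functional | Daily inpatient ROM | physical therapist | none |

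**Domains.** The RN is named as collector in 4 of 4. The PI is named as supervisor in the psychosocial and functional domains and for the mapping, and shares the preoperative neurophysiologic tests with the Co-PI.

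**Hypothesis 1 risk factors.** There are five. Four (thermal sensitivity, anxiety, catastrophizing, hyperalgesia area) are explicitly assigned to the RN. For the fifth, postoperative pain intensity, RN involvement can only be inferred from the NRS instructions in the pre-surgery section.

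**Masking.** No section masks the RN or PI to earlier scores or names a separate 6-month assessor. *Data collection and management* limits access to research personnel as a group, without restriction by domain or time. The documents do not say who scores the forms.

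**Which measures are exposed.** Mapping, StEP and ROM depend on how the examiner stimulates, prompts or reads. The NRS is asked for verbally by someone who, under *Discharge from hospital* and *Postoperative Follow-up*, has been querying the same patients about pain and medication up to 3 months. The questionnaires are answered by the patient and are much less exposed.

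**Sensitivity of the outcome (illustration only).** PPP needs an NRS of at least 4, and *General statistical analysis* reports modes of 0 and 3 in the preliminary survey, so the non-zero mode lies one point below the cut-off. The power section gives 46 PPP cases among 259 patients at one year: 46/259 = 17.8%. If five patients moved up across the cut-off, cases would rise by 5/46 = 10.9%, to 51/259 = 19.7%. The five is an assumed number. The sum shows that small shifts matter; it does not estimate bias.

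**The case against.** The strongest reply has four parts.

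*There is no contradiction.* The provision binds co-investigators, and the RN is never called one. It also speaks of reducing bias, not removing it. This stands. A reader might infer that the plan breaks its own rule, or that it has no protection at all; neither follows. Some separation remains: co-investigator surgeons review radiographs, orthopedic evaluation of persistent pain bears on the exclusion of other causes that PPP requires, and a physical therapist records daily inpatient ROM.

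*Procedures are standardised and largely patient-reported.* The NRS has scripted wording. The thermal test has a fixed ramp, temperature and duration, and averages four patient ratings. Mapping uses one filament, fixed steps, closed eyes and digital planimetry. This narrows the route for bias but does not close it: at the bedside the examiner still applies the filament and marks the point at which the patient reports a change.

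*Bias toward the hypotheses needs knowledge and recall.* The RN would have to know, remember and act on predictor scores up to six months later, and nothing says the RN scores the forms or consults earlier results. This also stands. Inflation of the associations is plausible, but the documents do not establish it.

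*Earlier pain data cannot be withheld from the person who collects them.* Correct, and it limits what any remedy with existing staff can achieve.

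**Conclusion.** The concern holds in a limited form. The stated safeguard does not reach the people who take the measurements: the RN role collects in all four domains, including four of the five Hypothesis 1 risk factors by explicit assignment and the 6-month NRS behind PPP, in up to 300 patients. The PI's supervision spans three domains in whole or in part.

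Three stronger statements are tempting and go too far. That all five risk factors pass through the RN is not stated, because no collector is named for the 4-hourly inpatient NRS. That a single individual does everything is not stated either: the RN is a role, and the number of people filling it is not given. That the resulting bias favours the hypotheses, or has any particular size, cannot be shown from the documents.

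The conclusion assumes that the measurement sections describe actual practice and that no masking procedure exists outside these documents. The planned analysis can proceed, but the blinding paragraph should not stand as the account of how measurement bias is handled.

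**What to change.** With existing staff:

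1. Reword *Blinding of data* to say that the separation applies to co-investigators only and that the RN and PI are not masked across domains. State who performs the 6-month StEP and who records the 4-hourly NRS.
2. Have the biostatistician score the PCS and STAI, and withhold those scores from the RN and PI until the patient's 6-month NRS is recorded. Leave the BDI-II available for clinical review.
3. Have the patient write down the 6-month NRS, using the existing scripted wording, before StEP begins.
4. Run planimetry on templates identified by code, without pain or questionnaire data. The digital planimetry and subject-ID indexing already in the plan support this.

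The cost is a revised paragraph and a small data-handling step. Masking remains partial: the RN still knows the thermal results and the pain history, and coded templates protect only the area calculation, not the bedside mapping. Masking the 6-month assessor to that history would need another person. Report the remaining lack of masking as a limitation.
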